9.2.1.4.3. Time to death, tracheostomy, or permanent assisted mechanical ventilation

(≥ 23 hours/day):

The third Key secondary endpoint is time to death, tracheostomy, or permanent assisted mechanical ventilation (≥ 23 hours/day). The analysis of this endpoint will be performed using all randomized analysis set. All available time to event data regardless of use of additional/new AMX0035 treatment (ICE1) drug and all available time to event regardless of early discontinuation (ICE2) will be included. The time to first onset (TIMETO1) of death, tracheostomy or permanent assisted mechanical ventilation will be analyzed using SAS LIFETEST procedure and the comparison between oral edaravone 105 mg daily versus oral edaravone 105 mg on/off regimen will be performed using the log rank test. This endpoint will be summarized using the number of events and percentage and displayed by Kaplan-Meier estimates with 95% CI stratified by treatment group. The decomposition of each event will be descriptively summarized.

The SAS code planned for the analysis is outlined below.

[REDACTED]

The following analyses will be used as sensitivity for the above log rank test:

- 1) Cox proportional hazard regression model will be employed for time to death, tracheostomy, or permanent assisted mechanical ventilation (TIMETO1) with terms for treatment (TREAT) as explanatory variable and baseline ALSFRS-R score (BASE), randomization strata of ALSFRS-R rate of decline (DR) score during the screening period (2 levels strata of -1,-2 or -3,-4) and geographical region - GR (3 levels strata of Europe, America or Asia Pacific) as covariates. The following SAS code will be used:

[REDACTED]

Statistical Analysis Plan Protocol No. MT-1186-A02

Mitsubishi Tanabe Pharma America, Inc.

a) The adequacy of the proportional hazards assumption will be confirmed by including a time dependent covariate of edaravone 105 mg once daily (as dummy variable) by log (time) interaction (TREAT0T) in the primary analysis model and testing it in 5% level. The following SAS code will be used:

A large rectangular area of the document has been completely blacked out, obscuring several lines of text.

**9.2.1.4.4. Time to death or permanent assisted mechanical ventilation (≥ 23 hours/day):**

The fourth Key secondary endpoint is time to death, or permanent assisted mechanical ventilation. The analysis of this endpoint will be performed using all randomized set. All available time to event data regardless of use of additional/new AMX0035 treatment (ICE1) drug and all available time to event data regardless of early discontinuation (ICE2) will be included. The stratified Log-rank test and Cox proportional hazard regression model as specified for the third key secondary endpoint will be used for this endpoint as well.

9.2.1.4.5. Time to death:

The fifth Key secondary endpoint is time to death. The analysis of this endpoint will be performed using all randomized set. All available time to event data regardless of use of additional/new AMX0035 treatment (ICE1) drug and all available time to event data regardless of early discontinuation (ICE2) will be included. The stratified Log-rank test and Cox proportional hazard regression model as specified for the third key secondary endpoint will be

used for this endpoint as well.

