#### 17.4.5.4 Efficacy Analyses for Key Secondary Efficacy Endpoints

The following key secondary endpoints will be inferentially analyzed in the following specified order to maintain the overall Type I error. Endpoints with continuous values will be analyzed using the same method (MMRM) as for the primary efficacy endpoint. Time to death, tracheostomy, or permanent assisted mechanical ventilation (≥23 hours/day) will be analyzed using Kaplan-Meier estimates and 95% CIs. The comparison between Treatment Group 2 versus Treatment Group 1 will be performed using the log rank test. Subjects without any events during treatment will be right censored at the date of last study visit.

- 1. Change from baseline in % SVC to Week 48
- 2. Change from baseline in ALSAQ40 to Week 48
- 3. Time to death, tracheostomy, or permanent assisted mechanical ventilation (>23 hours/day)
- 4. Time to death or permanent assisted mechanical ventilation (≥23 hours/day)
- 5. Time to death

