4. STUDY DESIGN

4.1. Study Design

This is a Phase 3b, multicenter, double-blind, parallel group, randomized, study that will evaluate the efficacy and safety of 2 treatment regimens of edaravone for a period of 48 weeks in subjects with ALS as follows:

- Group 1: Edaravone 105 mg oral dose once daily for 48 weeks
- Group 2: Edaravone 105 mg oral dose in for 14 days, followed by a 14-day placebo. Subsequently, repeat edaravone 105 mg oral dose in for 10 days followed by 18-day placebo (regimen denoted as on/off).

Eligible subjects will be randomized at baseline in a 1:1 ratio to receive 1 of 2 treatment groups. Randomization will be stratified according to ALSFRS-R rate of decline score for 8 weeks screening period (2 levels strata of -1,-2 or -3,-4) and geographical region (3 levels strata of Europe, America or Asia Pacific).

Concomitant use of riluzole is permitted when the doses and regimens will remain unchanged from the day of evaluation of ALSFRS-R at the screening visit, through the end-of-treatment (EOT) or early termination (ET). Although dose reduction, dose interruption or discontinuation due to the onset of AEs, progression of dysphagia, or gastrostomy while on oral edaravone 105 mg are allowed, it is prohibited to initiate the use of riluzole. Subjects who initiate riluzole therapy de-novo during the treatment period will be discontinued from the study. The use of AMX0035 will be allowed for patients in the event that it becomes commercially available via prescription in their respective country. AMX0035 should be taken at least 1 hour after MT-1186.

This study consists of a screening period of 8 weeks, a double blind treatment period of 48 weeks, and a safety follow-up period of 2 weeks. A schedule of assessment of all study procedures is provided in Table 1.

- **Screening period:** Screening assessments will be performed up to 8 weeks (\pm 7 days) prior to Day 1. All screening evaluations must be completed and reviewed to confirm that potential subjects meet all eligibility criteria. If a subject has not met all eligibility criteria at the end of the screening period, the subject will be registered as a screen fail. Screen fail subjects may be eligible for re-screening 1 time.
- **Double-blind Treatment Period:** Subjects who successfully complete the screening period will return to the study clinic on Day 1 in a fasting state (eg, without breakfast) and inclusion

Statistical Analysis Plan
Protocol No. MT-1186-A02

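### SAP 9.2.1.4.3 names a plain log-rank test for H04, the H05 and H06 sections call that same test stratified, and no readable text names the strata

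*SAP*

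**What the plan says.** - **H04, SAP 9.2.1.4.3.** The test is given as: "the comparison between oral edaravone 105 mg daily versus oral edaravone 105 mg on/off regimen will be performed using the log rank test". The analysis is run in SAS LIFETEST and the code is redacted. In the readable text the word stratified describes only the display: "Kaplan-Meier estimates with 95% CI stratified by treatment group".
- **H04, protocol 17.4.5.4.** "The comparison between Treatment Group 2 versus Treatment Group 1 will be performed using the log rank test". No strata are named.
- **H05 and H06, SAP 9.2.1.4.4 and 9.2.1.4.5.** Both sections use the same phrase: "The stratified Log-rank test and Cox proportional hazard regression model as specified for the third key secondary endpoint".
- **Cox model, SAP 9.2.1.4.3.** It is adjusted for baseline ALSFRS-R and both randomisation factors, but its role is secondary: "The following analyses will be used as sensitivity for the above log rank test".
- **Randomisation, SAP 4.1.** "Randomization will be stratified according to ALSFRS-R rate of decline score for 8 weeks screening period", and also by region. That gives 2 decline categories × 3 regions = 6 cells, with 1:1 allocation.
- **Testing order, SAP 7.3.** H01 to H06 form a fixed sequence, and each hypothesis is examined only if the one before it reaches p ≤ 0.05.
- **Declared changes, SAP section 11.** No move from the protocol's log-rank test to a stratified one is listed.

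**The concern.** H05 and H06 take their test by reference from H04, and the description in the reference does not match the readable text it points to. H04 belongs to the confirmatory family and decides whether H05 and H06, including time to death, are tested at all. With few events, the stratified and unstratified p-values can fall on opposite sides of 0.05. A gatekeeping test that can be read two ways leaves open which p-value governs.

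There is also a possible efficiency cost. When allocation is balanced within prognostic strata and the test ignores them, the test's variance is overstated, so its size falls below nominal and some power is lost. The MMRM for the continuous key secondary endpoints and the Cox model both adjust for the randomisation factors. A plain log-rank test would be the exception.

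**Working it through.** **1. The texts side by side**

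| Place | Hypothesis | Test named | Strata named |
|---|---|---|---|
| Protocol 17.4.5.4 | H04 | log-rank | none |
| SAP 9.2.1.4.3 | H04 | log-rank (code redacted) | none readable |
| SAP 9.2.1.4.4 | H05 | stratified log-rank, by reference to H04 | none |
| SAP 9.2.1.4.5 | H06 | stratified log-rank, by reference to H04 | none |
| SAP 9.2.1.5.7 | King's stage | stratified log-rank | none |

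There are two possibilities. If the redacted H04 code is unstratified, the reference in 9.2.1.4.4 and 9.2.1.4.5 points to a test that does not exist. If the code is stratified, it adds something that neither the prose of 9.2.1.4.3 nor the protocol states, and section 11 does not declare it. The text needs correcting in either case.

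**2. The plan's power figure**

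Inputs from SAP 4.2 and protocol 17.2: 190 per arm, HR 0.3, 90% control survival at Week 48, two-sided 5%, stated power 78%.

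Expected events without dropout: 190 × (1 − 0.9) + 190 × (1 − 0.9^0.3) = 19.0 + 5.9 = 24.9.

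- Freedman: Φ(√24.9 × 0.7/1.3 − 1.96) = 76.7%.
- Exponential (Lachin-Foulkes): 76.9%.
- Two proportions, 10% against 3.1%: 77.6%.
- Schoenfeld: 85.2% without dropout. With 30% exponential dropout (21.0 events) it gives 78.8%, while Freedman falls to 69.4%.

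The 78% is therefore reproduced to within 2 points without dropout. The 30% dropout is stated only for the t-test calculation. All these formulas are unstratified.

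**3. What stratification is worth at the planned inputs**

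The simulation used 380 patients balanced within the six cells, average control survival 90%, no dropout and 8,000 trials per scenario, with both tests applied to the same data. The documents give neither the sizes nor the prognostic strength of the strata. Assumed here: decline categories 60/40, regions 30/40/30, and these hazard multipliers:

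- moderate: fast decline ×2, regions 1/1.3/0.8
- strong: ×4, regions 1/1.5/0.5
- very strong: ×8, regions 1/2/0.3

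| Strata | Power at HR 0.3, unstratified | Power, stratified | Difference (points) | Size, unstratified | Size, stratified |
|---|---|---|---|---|---|
| Not prognostic | 80.13% | 80.35% | 0.2 | 4.89% | 4.91% |
| Moderate | 78.86% | 79.20% | 0.3 | 4.88% | 4.95% |
| Strong | 77.75% | 79.33% | 1.6 | 4.34% | 5.01% |
| Very strong | 77.76% | 81.05% | 3.3 | 3.20% | 4.85% |

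The Monte Carlo standard error of one power estimate is √(0.79 × 0.21/8000) ≈ 0.46 points, and of one size estimate √(0.05 × 0.95/8000) ≈ 0.24 points. The first two rows therefore show no material difference.

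**4. Sparse cells**

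24.9 events over 6 cells is about 4 per cell on average, and fewer in the smaller cells.

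**The case against.** The strongest reply is that the plan may already be right. The H04 code is redacted, a STRATA statement could sit there, and 9.2.1.4.4 itself describes the H04 test as stratified. That stands. A reader might infer that H04 is tested unstratified and that the gate to H05 and H06 is therefore conservative. The documents do not support this, because text removed by redaction is not missing from the plan.

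The reply can add three things, all of which also stand:

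- A plain log-rank test is valid and is what the protocol prespecifies. An adjusted Cox model is already planned as a sensitivity analysis.
- Prognostic strength is assumed. That the other models adjust for decline rate and region reflects their use in randomisation and is not evidence of a survival effect. Larger losses appear only away from the plan's inputs. With 20% control events, HR 0.5, decline hazard ×4 and region ×2 per step, simulated power is 66% unstratified against 71% stratified, but those multipliers imply a 4 × 2 × 2 = 16-fold hazard range across cells.
- H04 is reached only if H01, H02 and H03 all succeed, so any lost power matters only then.

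None of this removes the mismatch in wording or supplies the missing strata.

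**Conclusion.** The SAP is internally inconsistent on the log-rank test for H04, and the readable text leaves the strata for H04 to H06 unstated. Whether H04 is actually stratified cannot be determined.

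A loss arises only if H04 is unstratified and the randomisation factors are prognostic. It is then mild at HR 0.3 and 90% control survival: about 0.3, 1.6 and 3.3 points of power for moderate, strong and very strong strata, with size 4.9%, 4.3% and 3.2%. These figures rest on the assumed strata sizes and multipliers and on no dropout. If the strata are not prognostic, nothing is lost.

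A reader might also infer a threat to the family-wise error rate. There is none from the choice of test as such, because unstratified size did not exceed 5% in any scenario. A reader might also take the decline and region strata as already specified for H05 and H06, but those sections name none. The case for a change rests mainly on having one unambiguous, prespecified p-value at a gate.

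**What to change.** Before database lock:

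1. In SAP 9.2.1.4.3, state that H04 is tested with a log-rank test stratified by the two randomisation factors: decline (−1, −2 or −3, −4) and region.
2. Add a pooling rule for sparse cells, fixed in advance and applied to event counts combined over arms. One form is to drop region and stratify by decline alone when any cell falls below a stated number of events.
3. Use identical wording in 9.2.1.4.4 and 9.2.1.4.5, and name the strata for the King's stage analysis in 9.2.1.5.7.
4. Keep the unstratified log-rank test as a sensitivity analysis.
5. List the change from protocol 17.4.5.4 in SAP section 11.

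If the redacted code is already stratified this way, only the text and the section 11 entry change. Otherwise the cost is a few sentences and one line of code. Stratifying lost no power in any scenario above. The downside is small: sparse cells, which the pooling rule addresses, and one declared departure from the protocol.

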9.2.1.5. Other Secondary Efficacy Analyses

All available data regardless of use of additional/new AMX0035 treatment (ICE1) drug and all available data up to early discontinuation (ICE2) will be included. For analysis of King's ALS Clinical Stage, if death after early discontinuation (ICE2) was occurred, the death event will be included.

9.2.1.5.1. Changes from baseline in ALSFRS-R score at Weeks 4, 8, 12, 24, 36 and 48

The Change from baseline in ALSFRS-R score at Weeks 4, 8, 12, 24, 36 and 48 will be analyzed using the similar model as specified for the 1st key secondary analysis replacing the %SVC at baseline covariate with ALSFRS-R at baseline. The LSMEANS estimates for the mean change from baseline to Weeks 4, 8, 12, 24 and 36 and 48, as well as the difference of the estimates between oral edaravone 105 mg daily versus oral edaravone 105 mg on/off regimen will be displayed with their corresponding standard errors, p-values, and 95% CI. This endpoint will be analyzed using the FAS. The same analysis will be performed for ALSFRS-R subdomains.

9.2.1.5.2. Change from screening and baseline in %Forced Vital Capacity (%FVC)

The Change from baseline in %FVC score at Weeks 24, and 48 will be analyzed using the similar model as specified for the 1st key secondary analysis replacing the %SVC at baseline covariate with %FVC at baseline. The LSMEANS estimates for the mean change from baseline to Weeks 24 and 48, as well as the difference of the estimates between oral edaravone 105 mg daily versus oral edaravone 105 mg on/off regimen will be displayed with their corresponding standard errors, p-values, and 95% CI. This endpoint will be analyzed using the FAS. In addition, frequency counts and percent for categorical %FVC: 70%<=%FVC, 50%<%FVC<70% and %FVC <=50% will be displayed at each visit.

9.2.1.5.3. Change from baseline in %Slow Vital Capacity to Weeks 4, 8, 12, 24, and 36

The Change from baseline in %SVC score at Weeks 4, 8, 12, 24, and 36 will be analyzed using the same model as specified for the first Key secondary analysis. The LSMEANS estimates for the mean change from baseline to Weeks 4, 8, 12, 24 and 36, as well as the difference of the estimates between oral edaravone 105 mg daily versus oral edaravone 105 mg on/off regimen will be displayed with their corresponding standard errors, p-values, and 95% CI. This endpoint will be analyzed using the FAS.

9.2.1.5.4. Change from baseline in ALS Assessment Questionnaire (ALSAQ)40 to Week 24

The Change from baseline in ALSAQ40 score at week 24 will be analyzed using the same model as specified for the second Key secondary analysis. The LSMEANS estimates for the mean change from baseline to weeks 24 as well as the difference of the estimates between oral edaravone 105 mg daily versus oral edaravone 105 mg on/off regimen will be displayed with their corresponding standard errors, p-values, and 95% CI. This endpoint will be analyzed using the FAS.

9.2.1.5.5. Change from baseline in Body Weight at weeks 4, 8, 12, 24, 36 and 48

The Change from baseline in Body Weight score at Weeks 4, 8, 12, 24, 36 and 48 will be analyzed using the similar model as specified for the 1st key secondary analysis replacing the %SVC at baseline covariate with Body Weight at baseline. The LSMEANS estimates for the mean change from baseline to Weeks 4, 8, 12, 24, 36 and 48, as well as the difference of the estimates between oral edaravone 105 mg daily versus oral edaravone 105 mg on/off regimen will be displayed with their corresponding standard errors, p-values, and 95% CI. This endpoint will be analyzed using the FAS.

9.2.1.5.6. Combined Assessment of Function and Survival Score (CAFS) at Week 24

The CAFS at week 24 will be analyzed using the same model as specified for primary analysis in primary endpoint. The estimate of the treatment differences at week 24 corresponding 95% CIs and p-values will be calculated. This endpoint will be analyzed using the FAS and this analysis will be done for the following subjects only.

Subjects who was dead until Week 24 (Days <=211). Subjects who survived with available ALSFR-R until Week 24

Subjects who discontinued before Week 24 and who have missing ALSFR-R at Week 24.

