6.1.2. Efficacy Full Analysis Set (FAS)

The FAS is defined as all randomized subjects who received at least 1 dose of study medication. Subjects in the FAS will be grouped and analyzed based on the planned treatment allocated (as randomized). Efficacy endpoints will be analyzed using the FAS.

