8.4.2. Efficacy Measures

8.4.2.1. Combined Assessment of Function and Survival Score (CAFS)

CAFS ranks patients' clinical outcomes based on survival time and change in the ALSFRS-R score¹⁰.

CAFS Scoring:

To calculate a patient's CAFS, each patient is compared individually to all other patients in the study. The summary score for each patient is the sum of the comparisons (1, 0, 1) against all other patients (Figure 2). For each pairwise comparison of patients, the patient who fares better earns a point, and the one who fares worse loses a point. In the case of a tie, no points are added or subtracted. If both participants die, the one surviving longer fared better; if only one survives then that patient fared better; and if both participants survive, the one with the smaller decline in ALSFRS-R from baseline to week 48 fared better. If a participant discontinues early or ALSFRS-R at week 48 are missing, the participant will be treated as alive at week 48 and the ALSFRS-R at week 48 will be imputed missing using multiple imputation under missing mechanism assumption.

CAFS Ranking:

Next, patients' summary scores are ranked (Figure 3). In general, the ranking has the following characteristics:

- (1) The first patient who dies will have the lowest score and is ranked the lowest;
- (2) the last to die is ranked above all others who die;

- (3) Among survivors, the patient with the greatest decline in ALSFRS-R is ranked just above the last patient who died;
- (4) The surviving patients with the least decline in ALSFRS-R is ranked highest.

[REDACTED]

[REDACTED]

The average rank score is then calculated for each treatment group. A higher mean rank score indicates that participants in that treatment group, on average, fared better.

Figure 2: [REDACTED]

8.4.2.2. %Slow Vital Capacity (%SVC) Change from Baseline at week 4, 8, 12, 24, 36 and 48

SVC measurements will be conducted in clinic at around the same time of day where possible with the subject in sitting upright position. Subjects should make at least 3 attempts to generate acceptable and reproducible SVC data. If subjects cannot complete all three attempts due to disease progression or other reasons, it will not be considered a protocol deviation. The best value will be selected and will be recorded in the eCRF.

8.4.2.3. ALSAQ40 Change from Baseline at week 24 and 48

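### The Week 24 CAFS is said to use the FAS, but its list of admitted subjects leaves out living, on-study subjects with no Week 24 ALSFRS-R score

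*SAP*

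**What the plan says.** SAP 9.2.1.5.6 (CAFS at Week 24) applies the primary analysis model and sets the population in one sentence: "This endpoint will be analyzed using the FAS and this analysis will be done for the following subjects only". Three groups follow:

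1. "Subjects who was dead until Week 24 (Days <=211")
2. "Subjects who survived with available ALSFR-R until Week 24"
3. "Subjects who discontinued before Week 24 and who have missing ALSFR-R at Week 24"

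Four other places in the SAP bear on this:

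- Section 6.1.2: "The FAS is defined as all randomized subjects who received at least 1 dose of study medication".
- Section 8.4.2.1, on how CAFS is scored: "each patient is compared individually to all other patients in the study". On missing data at Week 48: "If a participant discontinues early or ALSFRS-R at week 48 are missing, the participant will be treated as alive at week 48", with the missing score then multiply imputed.
- Section 8.5, Table 5: Week 24 has nominal Day 169 and an analysis window of Day 128 to 211.
- Section 11: the requirement for post-randomization efficacy data was removed from the FAS definition, so that everyone randomized and dosed is analyzed whether or not such data exist.

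**The concern.** The population sentence contradicts itself. Its first half takes in every randomized and dosed subject. Its second half admits only the listed groups, and the third group joins discontinuation and a missing score with *and*. A subject who stays on study but has no usable Week 24 score does not satisfy that condition.

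Dropping such subjects would make the Week 24 result partly a complete-case analysis under an FAS label. In a progressive disease, missing a clinic visit may be related to how the subject is doing, and the SAP's own answer to this at Week 48 is imputation under MAR. CAFS is also a relative score: each subject is compared with every other, so removing one changes the pool against which all the rest are ranked. Week 24 and Week 48 CAFS results printed in the same report would then rest on different populations and different missing-data rules, with nothing in the text to say so.

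**Working it through.** No power or sample-size formula applies. The check is whether the three groups cover the FAS.

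**Step 1: the window.** Nominal Week 24 is 24 × 7 + 1 = Day 169, as in Table 5. The window of Day 128 to 211 spans 211 − 128 + 1 = 84 days. In the global schedule (Protocol Table 1), ALSFRS-R is taken in clinic at Weeks 12, 24 and 36, and Weeks 20 and 28 are telephone visits without it. The window therefore holds one scheduled ALSFRS-R. A late or rescheduled assessment up to Day 211 still counts.

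**Step 2: cross-classify the FAS** by death by Day 211, a score in the window, and discontinuation before Week 24.

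| Dead by Day 211 | ALSFRS-R in Day 128–211 | Discontinued before Week 24 | SAP 9.2.1.5.6 | Week 48 rule applied at Week 24 |
|---|---|---|---|---|
| Yes | either | either | Group 1 | Ranked as a death |
| No | Yes | either | Group 2 | Ranked on observed score |
| No | No | Yes | Group 3 | Imputed |
| No | No | No | **None** | Imputed |

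The fourth row is the gap. It includes a subject who misses Week 24 and returns at Week 36, and one who misses Week 24 and dies after Day 211.

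**Step 3: compare the connectives.** Group 3 requires discontinuation *and* a missing score. The Week 48 rule in 8.4.2.1 is triggered by early discontinuation *or* a missing score. Replacing *and* with *or* in Group 3 fills the fourth row, so the gap comes entirely from that word combined with the restriction to listed groups.

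**Step 4: the Day 211 cutoff.** Week 36 is Day 253, and (169 + 253)/2 = 211. The cutoff is thus the midpoint between the two visits and the upper limit of the Week 24 window in Table 5. It lies 211 − 169 = 42 days, or 6 weeks, after nominal Week 24.

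**Step 5: size.** The number in the fourth row cannot be derived. The 30% dropout assumption in SAP 4.2 concerns loss up to Week 48, not intermittent missed visits, and no other rate is given.

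**The case against.** **The wording may be loose rather than exclusionary.** The second group could be read as survivors with any ALSFRS-R up to Week 24, which would admit an on-study subject with earlier scores. But early discontinuers with any earlier score would then already be in that group, leaving the third largely redundant. The narrow reading is the natural one. If both readings are possible, two programmers could produce different analysis populations, which is itself a reason to fix the text.

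**Few subjects are at stake.** This stands. The window is 84 days wide, Protocol 10.1 allows questionnaires by telephone when COVID-19 restricts visits, and deaths by Day 211 are already captured.

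**Nothing confirmatory depends on it.** This also stands. SAP 3.3.3 lists the endpoint among the other secondary ones and SAP 7.3 leaves it out of the fixed sequence. The SAP does not present it as support for the primary analysis; analyses with that purpose are in 9.2.1.3.

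**Part of the CAFS text is blacked out.** True, but the Week 48 missing-data rule and the Week 24 list are both legible, and the conflict lies between those two.

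**Conclusion.** The population statement needs correcting. As written, it excludes some FAS subjects because a score is missing, whereas the SAP imputes for the same situation at Week 48. This rests on the narrow reading of the second group. The number of subjects is unknown and probably small, the direction of any effect cannot be stated, and the consequence is confined to one other secondary endpoint.

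A reader might go further and infer that the Day 211 cutoff is a mistake, on the ground that it mixes 24-week function with 30-week mortality. The documents do not support that. Day 211 closes the SAP's own Week 24 window, and an ALSFRS-R taken as late as that day can also serve as the Week 24 value. SAP 8.4.2.8 likewise uses the end of the visit window when assigning deaths in King's staging.

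The choice does affect how many deaths are counted. Under a constant hazard and an assumed 90% survival at Week 48, the expected deaths per 190 subjects are:

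- by Day 169: 190 × (1 − 0.9^(168/336)) = 9.7
- by Day 211: 190 × (1 − 0.9^(210/336)) = 12.1

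That is about 24% more, and the ratio hardly moves for 85% to 95% survival. SAP 4.2 attaches the 90% to the control group and to death, tracheostomy or permanent ventilation, so using it for death alone is an assumption. These figures describe a prespecified convention. They do not measure misranking, because some subjects who die on Days 170 to 211 would have no Week 24 score to discard.

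**What to change.** In SAP 9.2.1.5.6, delete the restriction to listed groups. State instead that all FAS subjects are ranked, and that any subject not counted as dead by Day 211 who has no ALSFRS-R in the Week 24 window is treated as alive, with the score multiply imputed as in the primary analysis (9.2.1.1). Changing *and* to *or* in the third group would close the same gap. Deletion is cleaner, because with *or* an early discontinuer who has a score in the window would fall in two groups.

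Leave the death cutoff as it is. A table footnote saying that deaths are counted to Day 211 would be enough.

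The cost is one or two sentences before database lock. No new data are needed, and the primary imputation approach can be reused.
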